#### **A4. RESEARCH DESIGN AND METHODS**

*Aim 1 consists of an analysis of data extracted from the EHR to identify risk profiles (scores) and determine which patients are unlikely to engage in care for depression. These risk scores will be used to select patients for a proposed intervention that will be developed in Aim 2 and subjected to a formative evaluation in Aim 3. The intervention is technology-based and includes automated symptom assessment with emotional and practical support texts to provide interim support to Veterans referred to mental health care who are awaiting their initial mental health treatment visit.*

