Treatment initiation	A primary or secondary stop code showing a visit in mental health (with a psychologist or psychiatrist) or primary care AND an ICD9 for depression diagnosis.

Sampling plan and data extraction and processing:

**Data source and cohort selection.** We will use data from the VA Corporate Data Warehouse (CDW), a centralized data repository which contains electronic medical records of all Veteran patients who receive care through the VHA. The patient cohort (N = 88,456) used for completion of Aim 1 includes 1) OEF/OIF Veteran patients with a PHQ9  $\geq$ , 2) who were not already in treatment for depression prior to this PHQ9 assessment, 3) were never diagnosed with bipolar, personality, psychotic, and pervasive developmental disorders to be consistent with the National Committee on Quality Assurance measure of quality of care, HEDIS (HEDIS, 2018), as well as substance dependence or patients who are in treatment for substance related disorders at the time of recruitment. The exclusion criteria are based on the fact that the presence of these disorders may result in divergent treatment practices compared to unipolar depression in the absence of these conditions. Our primary outcome, treatment initiation, is conceptualized as a combination of service encounters with specialty mental health (psychologists, psychiatrists) or primary care providers charted into the patients' VHA medical records (excluding assessments) that were associated with any depressive disorder diagnosis. Our data are already IRB exempt, R&D and DART approved, and have already been extracted.

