**Data processing.** Data will be initially checked for out of range values and missing data where appropriate through plotting and descriptive analyses. Data will be transformed as needed. Logistic regression is relatively free of restrictions and can accommodate a mix of predictors (continuous, discrete, dichotomous) (Tabachnick & Fidell, 2007). *With continuous predictors, the assumption is that there is a monotonic relationship (increase or decrease) between the predictor variable and odds of the binary outcome (i.e. engagement or lack of engagement in care). The functional of this linear assumption can be evaluated by use categorical indicator variables as well as transformations of the continuous variable, such as a quadratic form. Multicollinearity will be tested using two approaches. First, we will explore correlations among IVs and exclude variables based on high correlations ( $> .65$ ). Second, we will examine the size of the standard error (SEs) relative to the beta coefficient for each predictor in the model. Large SEs will be indicative of potential multicollinearity. Residuals will be tested to identify possible outliers.*

Analysis plan:

**Modeling risk for lack of treatment engagement.** For all analyses, lack of treatment engagement is the main dependent variable and will be investigated using three related definitions based on the date in which a PHQ9 score  $\geq 10$  is identified in the EHR. Specifically, we will examine whether treatment is initiated within 3-months, 6-months, or 12-months from the date of the PHQ9 assessment. *Independent variables of interest will be extracted based on proposed framework, empirical evidence, and availability in the EHR (see Table 1), including insight from a select number of semi structured surveys collected prior to data analysis (described below).*

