*Data Analysis. First, descriptive analyses will be performed on all baseline patient characteristics extracted for all patients approached for study enrollment, including those who agreed and did not agree to participate. To compare these two groups, we will use student t-tests (for continuous variables) and chi-square analysis (for categorical variables). This information will be used to derive acceptability of the proposed intervention. Next, descriptive analyses will be performed on the baseline questionnaires collected from the group of participants enrolled. This will give us additional data about patient characteristics that may further refine our phenotypes or improve study feasibility in the future. Engagement will be derived from percentage of prompts completed per days of participation in the intervention. Finally, we will calculate rates of treatment initiation (and corresponding 95% confidence interval) and compare to the initiation rate identified in our recent study on the Aim 1 cohort. To compare study treatment initiation to rates observed in Aim 3 to those in Aim 1 sample we will calculate the 95% confidence interval (CI) for the difference score between proportions (see Franklin, 2007). A significant difference will be denoted if the 95% CI does not include zero (Cumming & Finch, 2005). I will use negative binomial regression which accounts for overdispersion if treatment initiation is low (Coxe, West, & Aiken, 2009).*

Qualitative interviews and analysis: The interviews will be conducted using a semi-structured interview guide (see Appendix 3) and the same methods as Aim 2 interviews and analysis. These interviews will focus on the user's experiences using the self-monitoring intervention. Feedback will be sought about the functionality of the intervention, its perceived use, and ways to enhance it. We will specifically inquire about patients' perceptions about the three parts of the intervention: the symptom self-monitoring, practical support (i.e., appointment reminders), and emotional support (i.e., encouragement). Patients will also be asked to provide suggestions for emotionally supportive messages patients may want to see as they prepare to attend mental health sessions. Qualitative data will be analyzed in the same manner as presented in Aim 2.

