An eHealth intervention to increase depression treatment initiation and adherence among veterans referred for mental health services (CDA 18-189)

NCT05990075

November 30, 2022

*Analysis plan:*

*Data processing.* Data will be checked for out of range values and missing data where appropriate through plotting and descriptive analyses. Finally, data will be transformed as needed to create the variables of interest (e.g. age of depression onset as age of first episode visible in the EHR). *Missing Data Strategies.* We will minimize the level of missing data (due to loss to follow-up, withdrawal, or missing assessments) to the extent possible. If missing data occur, I will assess the missing data mechanism for data missing due to loss to follow-up or withdrawal. I will compare baseline measures (e.g., demographics, clinical history, etc.) between subjects that have complete outcome data and those that do not using logistic regression. Multiple imputation will be used for missing data in conjunction with a pattern of missingness. Missing data will be evaluated on an ongoing basis and recruitment may be continued beyond the original sample to achieve the desired power for the proposed analyses. *Data Analysis.* First, descriptive analyses will be performed on all baseline patient characteristics extracted for all patients approached for study enrollment, including those who agreed and did not agree to participate. To compare these two groups, we will use student t-tests (for continuous variables) and chi-square analysis (for categorical variables). This information will be used to derive acceptability of the proposed intervention. Next, descriptive analyses will be performed on the baseline questionnaires collected from the group of participants enrolled. This will give us additional data about patient characteristics that may further refine our phenotypes or improve study feasibility in the future. Feasibility will be derived from percentage of prompts completed per days of participation in the intervention. Finally, we will calculate rates of treatment initiation (and corresponding 95% confidence interval) and compare to the initiation rate identified in the literature. To compare study treatment initiation to rates we will calculate the 95% confidence interval (CI) for the difference score between proportions (see Franklin, 2007). A significant difference will be denoted if the 95% CI does not include zero (Cumming & Finch, 2005).

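### Aim 3 plans negative binomial regression for a yes/no initiation outcome, and the Protocol and SAP describe the reference rate differently without carrying a time window into Aim 3 (minor)

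*Protocol*

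**What the plan says.** **Outcome.** Table 1 (Protocol, A4a) defines treatment initiation as "A primary or secondary stop code showing a visit in mental health (with a psychologist or psychiatrist) or primary care", together with a depression diagnosis code. The Data processing paragraph of A4a models the "odds of the binary outcome (i.e. engagement or lack of engagement in care". Aim 1 examines "whether treatment is initiated within 3-months, 6-months, or 12-months from the date of the PHQ9 assessment".

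**Aim 3 analysis.** Protocol A4c, Data Analysis, calculates the initiation rate with a 95% confidence interval and will "compare to the initiation rate identified in our recent study on the Aim 1 cohort". It calls the difference in proportions significant if its 95% interval excludes zero. It then adds: "I will use negative binomial regression which accounts for overdispersion if treatment initiation is low". No threshold for low is given.

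**SAP.** The Data Analysis text is nearly the same. However, it will "compare to the initiation rate identified in the literature", and it has no negative binomial sentence. It keeps the decision rule: "we will calculate the 95% confidence interval (CI) for the difference score between proportions".

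**Population.** The intervention is for "Veterans referred to mental health care who are awaiting their initial mental health treatment visit". A4a (risk score computation) and A4b (sampling plan) select patients for Aims 2 and 3 on a risk score for not initiating treatment. The Aim 3 sample is 15.

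**The concern.** Negative binomial regression is for counts whose variance exceeds their mean. A yes/no outcome has no such excess at any rate, low or high. The rule therefore names a model for a problem that cannot occur, and leaves the real small-count problem (few or no initiators among 15) without a suitable method.

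The comparator raises a separate question. A significant-difference statement needs one reference rate, measured over the same time and from the same starting point as the Aim 3 rate. The two documents describe the reference in different words. Neither says over what period, or from what date, initiation is counted for an Aim 3 patient. If these choices are left until the Aim 3 count is known, they can settle the answer.

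**Working it through.** The plan has no figure to reproduce here: n = 15 rests on convention for formative pilots, and the supplied text gives no reference rate.

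**1. No overdispersion.** For a 0/1 outcome with mean p, the variance is p(1-p), which is never above p.

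**2. The model collapses to Poisson.** Take x initiators among n, mean fixed at x/n, dispersion a, and u = a·x/n. The negative binomial log-likelihood is

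x·log(x/n) − x·(1+u)·log(1+u)/u.

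The second term grows with u, so the likelihood is highest at a = 0, which is Poisson. At 3/15 the values are −7.828 (a = 0), −7.858 (a = 0.1) and −8.110 (a = 1).

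**3. Size of the variance error.** This assumes an intercept-only model with model-based standard errors. The log-scale standard error is 1/sqrt(x) under Poisson and sqrt((1−p)/x) under the binomial, a ratio of 1/sqrt(1−p). Each log-scale interval is (x/15)·exp(±1.96·SE).

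| Initiators | SE ratio | Poisson limit | Binomial, log scale | Clopper-Pearson |
|---|---|---|---|---|
| 1/15 | 1.035 | 0.9-47.3% | 1.0-44.3% | 0.2-31.9% |
| 2/15 | 1.074 | 3.3-53.3% | 3.7-48.4% | 1.7-40.5% |
| 3/15 | 1.118 | 6.5-62.0% | 7.3-55.0% | 4.3-48.1% |

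The gap between the two log-scale columns is the variance error. The remaining distance to Clopper-Pearson comes from the log scale, not from the choice of count model.

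**4. No initiators.** At 0/15 the log of the estimate is not finite, and the Wald interval is 0 to 0. Clopper-Pearson gives 0-21.8% and Wilson 0-20.4%.

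**5. The comparator, side by side.**

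| | Protocol, Aim 1 | Protocol, Aim 3 | SAP |
|---|---|---|---|
| Source of reference | – | recent study on the Aim 1 cohort | literature |
| Window | 3, 6 or 12 months | not stated | not stated |
| Start | PHQ9 date | not stated | not stated |
| Patients | PHQ9 of 10 or more, not yet in treatment | also referred, and selected on risk score | not stated |

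Even if both documents mean the same study, Aim 1 defines three windows, so up to three rates could serve as the reference. An Aim 1 rate would also describe the whole cohort, whereas Aim 3 patients are chosen because they are predicted not to initiate.

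**The case against.** Several objections have force.

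- **The harm is small.** A reader might infer that the model fails badly in just the low-rate case for which it is reserved. The table shows the opposite: the variance error falls to 3.5% at 1/15. Having no estimate at 0/15 is not special to this model, since log-binomial and logistic regression share it. This stands and limits the point.
- **The regression may not replace anything.** The Protocol calculates the rate and the intervals unconditionally and does not say that the regression supersedes them. This also stands. The model is still unsuitable, and nothing else is offered for low counts.
- **Initiation might be a count.** The A4a cohort paragraph describes initiation as made up of service encounters, and a negative binomial model could suit a count of visits. But no count outcome is defined for Aim 3, and the sentence follows directly on a comparison of proportions.
- **The two references may be one.** A3a mentions a paper on treatment initiation from these data, placed in Appendix 4, which is not in the supplied text and may give a rate and a window. A reader might infer that the comparators differ, or that no rate exists. The documents establish neither; they show only that the wording differs and that the supplied text does not resolve it.
- **The interval method is cited.** Both documents cite a source for the interval of the difference. A reader might call the missing name a defect, but the cited method cannot be seen here, so that is not claimed.

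**Conclusion.** The negative binomial sentence is wrong as written: the outcome is binary, overdispersion cannot arise, and the fit reduces to Poisson. The resulting standard error is 3.5% to 11.8% too large for one to three initiators among 15, under an intercept-only fit with model-based standard errors. The low-rate case does need its own method, but a binomial one.

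The Protocol and SAP wording on the reference rate must be reconciled, and an Aim 3 window and start date are missing from the supplied text.

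How far the choice of reference matters can only be illustrated. If the references were 18.5% and 27%, 7/15 (Clopper-Pearson 21.3-73.4%) would be significantly above the first and not the second. Those figures are the ends of the range that Protocol A1 gives for any mental health care use. Neither document names them as initiation rates, so the example does not show that the planned comparison would in fact reverse.

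The point is minor. Aim 3 is formative, and initiation is not among the purposes listed in its design overview. Only the significant-difference statement is affected.

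**What to change.** 1. Delete the negative binomial sentence from Protocol A4c, Data Analysis. The SAP already omits it.
2. In both documents, state that at low counts the Aim 3 initiation rate has a Clopper-Pearson or Wilson 95% interval.
3. Make Protocol A4c and the SAP name the same reference: source, rate, denominator, time window and start date. Use the same window and start date for Aim 3, and fix all of this before any Aim 3 initiation result is known.
4. Take the reference from Aim 1 patients above the risk-score cut-off used to select Aim 3 patients. Otherwise report the comparison as descriptive. A rate from all 88,456 patients would be precise but not like for like. The Aim 1 cohort definition also does not require a referral, so some difference would remain and should be stated.
5. If the chosen reference has a small denominator, let its uncertainty enter the interval for the difference.

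**Cost.** Wording in two documents, plus one extra Aim 1 tabulation if the risk-matched rate is used. Clopper-Pearson is conservative: against an assumed 18.5% it needs 7/15 where Wilson needs 6/15, and against an assumed 27% it needs 9/15 rather than 8/15. In return, the chance of a false claim of higher initiation at 18.5% is 1.2% rather than 4.4%.

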#### **A5. DISSEMINATION AND IMPLEMENTATION PLAN.**

Our team has collaborations with operational partners ([name], CPHIMS, Clinical Director, Mobile Health Deployment and Evaluation, Office of Connected Care), clinical stakeholders ([name], Chief of Psychology at the Tampa VA; [name], Supervisory Psychologist for the Primary Care Mental Health Clinics), consultants ([name], [name], [name], [name]) and the Tampa Rehabilitation Outcomes Section, Research Service, Veteran Engagement Council to ensure successful dissemination of findings. Evidence derived from the proposed CDA will inform the applicant's ongoing program of research in mental health service utilization. We will publish findings and present at professional meetings, including the HSR&D Annual Meeting and psychology conferences with a mental health focus. Dissemination to stakeholder groups will be developed in collaboration with my mentors and consultants on this CDA. Findings will be ultimately used in the development of next stages in research, such as the development of a follow-up IIR (see A7 below).

#### **A6. PROJECT MANAGEMENT PLAN.**

I will direct overall implementation of the project with guidance from my four mentors and four consultants. I will: (a) supervise the data extraction and collection; (b) consult with experts to guide the intervention development; (c) conduct planned meetings to ensure achievement of benchmarks. The PI will contribute to data collection, data analysis, and interpretation. A research assistant will be hired to help with data collection and management along [name] and myself. I will oversee administrative duties (including IRB). In collaboration with my mentors, consultants, and support team I will interpret, report, and publish data during the proposed CDA.

#### **A7. SUMMARY AND FUTURE RESEARCH PROJECTS.**

This CDA will help to establish a foundation for future efficacy/effectiveness research for patient engagement interventions to increase treatment initiation and adherence among Veterans with depression. Before widespread dissemination and implementation of the proposed intervention, it is important to identify factors that may help further individualize this intervention and barriers to broad dissemination and implementation, as proposed in this CDA. From prior work in this area we know that complicated interventions take more time, require more expertise, and will be less appealing to end users. We hypothesize that the proposed intervention will be easier to implement and be more appealing for adoption in primary care. Finally, my relationships with local, front-line providers and national leaders in dissemination and clinical operations will be extremely helpful in conceptualizing such a rollout. The proposed intervention may help increase access for Veterans by increasing adherence to treatment with minimal effort from providers to remind and reschedule sessions. This type of intervention could also improve access by providing ample information about patients' symptoms and mood therefore possibly decreasing initial assessment and allowing clinicians to intervene in a timely manner.

**Future Project 1** (proposed HSR&D Merit in CDA year 3). An initial HSR&D Merit will be an efficacy/effectiveness RCT testing whether the eHealth intervention developed and piloted in the current CDA increases treatment initiation and adherence with a focus on treatment outcomes. The proposed RCT will be enhanced through a study design that includes both an active (i.e., engaging with technology) and passive control group (treatment as usual which entails waiting between referral and treatment initiation), more robust sample sizes, and if deemed appropriate, a pre-implementation qualitative aim designed to more thoroughly investigate implementation barriers and facilitators. Outcomes of the proposed Merit will include treatment initiation and adherence, as well as depression outcomes, such as increased awareness of depression, higher depression knowledge, and clear identification of treatment goals. **Future Project 2**. Although we are no longer using NLP in the proposed CDA, we have submitted an HSR&D Pilot and received promising feedback that indicates that a Merit is warranted. I will be revising this application with reviewer feedback and develop it into another HSR&D Merit. The proposed study will employ NLP to develop methods that reliably extract routinely reported patient characteristics by mental health care providers in clinical notes, as a promising route to identifying a clinical marker for treatment engagement and depression outcomes. We will develop the NLP system to determine consistency and variability of documentation across providers and facilities. These data will enable an examination of the value of this clinical marker for depression outcomes.

My proposed CDA and future projects represent the next stage in developing my program of research to implement behavioral treatments for depression within primary care settings in the VHA. The proposed research will also help to move the field of depression research forward by contributing to our understanding of depression management; it could result in new mental health care models for depression, decrease disease burden, and fill the gap in the current depression treatment guidelines.

Table 3. Timeline of CDA Research Activities (Years 1-5).

Research Activity*	Quarters	Year 1				Year 2				Year 3				Year 4				Year 5			
		1	2	3	4	1	2	3	4	1	2	3	4	1	2	3	4	1	2	3	4
Aim 1																					
IRB, R&D, train RA																					
Semi structured surveys of treatment barriers (PI)																					
Stage 1 analyses: regression models																					
Stage 2 analyses: machine learning																					
Secondary analyses for publications																					
Aim 2																					
Program Qualtrics intervention																					
Obtain Veteran patient input																					
Obtain Clinician input																					
Aim 3																					
Refine intervention																					
Recruit Veterans to pilot intervention																					
Intervention formative evaluation & pilot																					
Qualitative data analysis																					
Further evaluation and preparation of qualitative data for manuscripts																					
IIR 1: RCT (1 st submission)																					
IIR 2: NLP Merit (1 st submission)																					
IIR 3																					
Manuscripts**																					

\* Per HSR&D RFA: research funds are provided for years 1-3; years 4-5 are dedicated to dissemination and grant writing activities, setting up a sustainable research lab

\*\*based on manuscript productivity during postdoctoral fellowship: I published an average of 3 manuscripts per year.
